7.3.3.2. Evaluation of Drug Induced Serious Hepatotoxicity (eDISH)

A Hy’s law case refers to an increase in aminotransferase $> 3x$ the reference upper limit of normal (ULN), with bilirubin $> 2x$ ULN. Possible Hy’s law cases can be visualized with use of Evaluation of Drug Induced Serious Hepatotoxicity (eDISH) plots, a log-log scatter plot where the x-axis is the peak post-baseline ALT as a multiple of ULN, and the y-axis is the peak post-baseline total bilirubin as a multiple of ULN (Guo, 2009).

The following series of figures, adapted from [Teskaldet et al. \(2016\)](#), will be produced for the Safety Analysis Set.

1. Distribution of ULN of Liver Serum Enzymes. The ULN reference values used in each test (bilirubin, ALT, AST, and ALP) and their respective frequencies in percentiles.
2. Distribution of Baseline Liver Serum Enzymes for each test.
3. Distribution of Baseline Liver Serum Enzymes (xULN), for each test.
4. Status of Baseline Liver Serum Enzymes as Function of ULN. Baseline status categorized as normal, >1x, >1.5x, >2x, >3x, >5x, >10x.
5. eDISH plot for all patients.
6. eDISH plot by quadrant.
7. Panel of eDISH Quadrant Shift Plots at Baseline. Patients are color coded to correspond to the quadrant they belong in the eDISH plot. The data presented in the panel corresponds to each patients' Baseline value as a multiple of the ULN.
8. Panel of Shift Plots by eDISH Quadrants. Patients are color coded to correspond to the quadrant they belong in the eDISH plot. The data is presented as multiples of the Baseline value (BLN) rather than the ULN. The shift in peak post-baseline laboratory value is compared to each patients' Baseline value.
9. Panel of eDISH Shift Plots by eDISH Quadrants. The panels represent the on-treatment eDISH quadrants whereas the colored symbols represent the eDISH quadrants of the Baseline values (not post-baseline) as multiples of ULN.
10. Time Course of Liver Tests as xBLN & xULN.

7.3.3.3. Vital Signs

Actual values and changes from Baseline in vital signs (temperature, systolic and diastolic blood pressure, pulse, and respiratory rate) at each analysis visit will be summarized descriptively. Details for Baseline definition and analysis visit window can be referred to in [Appendix 9.4.4](#). Missing vital signs data will not be imputed and only scheduled assessments will be summarized in tables. When multiple records exist for a same vital sign parameter within the same analysis visit, the record closest to the target date will be used. If there are multiple records with the same distance from the target date, the latest record will be used. A summary for “Last Assessment” will be included for the last available post-baseline result for each patient. Summaries of change from Baseline by category in blood pressure and heart rate will also be created to allow detection of clinically relevant changes; these will be changes of ± 20 mmHg for systolic or diastolic blood pressure and ± 20 BPM for resting heart rate. A by-patient listing of vital signs will be presented, with both scheduled and unscheduled assessments included.

7.3.3.4. Electrocardiogram

Actual values and changes from Baseline in ECG data (heart rate, PR, QRS, QT, QTc, and QTcF intervals) at each visit will be summarized descriptively. Missing ECG data will not be imputed and only scheduled assessments will be summarized in tables.

Single 12-lead ECG results will be classified by the Investigator as “normal,” “abnormal, NCS,” or “abnormal, CS” and will be summarized in a table. Three-by-three contingency tables will be presented to summarize the shift from the Baseline category to the worst post-baseline value. Summary results will include the count and percentage of patients within each shift category.

The ECG results will also be presented in listings by patient and by visit.

7.3.3.5. Physical Examinations

Results of the abnormal physical examination will be presented in a summary by study visit and body system. Physical examination data (including height and weight) will also be listed at all visits.

7.3.3.6. Other Safety Parameters of Special Interest

No other safety events of special interest have been defined for this study.

7.4. Extension Period Analyses

Actual value and change from Baseline for efficacy endpoints will be analyzed using descriptive summary statistics. Efficacy analyses will be performed using the FA Set in the Extension Period.

Actual value and change from Baseline for safety endpoints will be analyzed using descriptive statistics. Safety analyses will be performed using the Safety Analysis Set in the Extension Period.

All data collected in the Extension Period will be fully listed in the same by-patient listing for the Treatment Period. The same Baseline will be used for both Treatment Period and Extension Period.

7.5. Interim Analyses

Marketing Authorization Application(s) may be submitted before all patients complete the Treatment Periods; therefore, interim analyses of safety data only or safety and efficacy data together may be performed to support these submissions. These analyses will be descriptive only, a full or a subset of the listed outputs will be provided as appropriate, and they will not include formal hypothesis testing and will not be used to adapt the study. These analyses will be performed for the disposition, demographics, Baseline characteristics, exposure, safety, primary, secondary, and exploratory objectives, if sufficient information is available.

9. APPENDICES

9.1. Protocol Schedule of Events

Please refer to Protocol Amendment 5 Section 1.3 [Table 1](#) and [Table 2](#) for schedule of activities.

9.2. Changes From Analyses Specified in the Previous Version of the SAP

Please refer to Section [4.2](#) in this SAP for changes from analyses specified in the previous version of the SAP.

9.3. Sample Size, Power, and Randomization

Using a t-test statistic, 24 patients in ALXN1840 will provide 92% power at a 1-sided significance level of 0.025 to detect a reduction of 228 µg Cu/g dry liver, with an SD of paired difference of 319, in Cu concentration.

Approximately 28 patients will be enrolled to accommodate a 15% dropout rate, such that approximately 24 evaluable patients complete the study.

9.4. Technical Specifications for Derived Variables

The following derived data will be calculated prior to the analysis.

9.4.1. Adverse Events

The analysis of AEs is described in detail in Section [7.3.2](#).

The TEAEs are AEs with onset on or after the first study drug dose. If the start date of an AE is partially or completely missing and the end (stop) date and time of the AE do not indicate that it occurred prior to the first dose, then the determination of treatment-emergent status will be based on the following:

- If the start year is after the year of the first study drug dose, then the AE is treatment-emergent; else,
- If the start year is the same as the year of the first study drug dose and
 - The start month is missing, then the AE is treatment-emergent; else if
 - The start month is present and is the same or after the month of the first study drug dose, then the AE is treatment-emergent; else,
- If the start date is completely missing, then the AE is treatment-emergent.

All other AEs are considered pre-treatment AEs.

9.4.1.1. Handling Missing/Partial AE Start Date

The missing or partial AE start date will be imputed for analysis as follows:

- If the year is not missing, but both day and month are missing and
 - If the year of the AE start date is the same as year of the first dose date, then impute AE start date to the first dose date.

- If the year of the AE start date is not the same as year of the first dose date, then impute the missing day and month of AE start date as June 15.
- If only the day of the AE start date is missing and
 - If the year of the AE start date has the same year and month parts as in the first dose date, then impute the AE start date to the first dose date.
 - If the AE start date has the same year and month parts as in the AE end date, and the day of the AE end date is smaller than 15, then impute the AE start date to the AE end date.
 - Otherwise, impute the missing day of the AE start date as 15.
- If the year is missing, leave the AE start date as missing.

After steps mentioned above, if the imputed AE start date is after the non-missing AE end date, then reset the AE start date to the AE end date.

If imputation results in a date prior to the birth date, then change the AE start date to be equal to the birth date.

If imputation results in a date after the death date, then change the AE start date to be equal to the death date.

Completely missing dates will not be imputed.

9.4.2. Age

Age will be presented as the number of years between the date of birth and the reference date. Age at enrollment will be calculated based on the informed consent date using the following formula:

$$\text{Age (year)} = \text{FLOOR}((\text{date of informed consent} - \text{date of birth})/365.25)$$

where FLOOR() function returns the integer part of the result.

In cases where only the month and year are provided for a date, the day for the date will be imputed as 15. The missing month will be imputed as June. In cases where the day is observed but the month is missing, the date will be imputed as June 15. In instances when the imputed reference date is earlier than the birth date, the birth date will be used as the reference date.

9.4.3. Analysis Relative Day

Analysis relative day is defined as the actual day relative to the first dose date of study drug. Specifically, the date of interest – the first dose date if the date of interest occurs prior to the first dose date and the date of interest – the first dose date + 1 if the date of interest occurs on or after the first dose date.

9.4.4. Analysis Visit Windowing

In the analysis of data summarized by visit, all data collection will be reassigned an analysis visit where data are scheduled for collection based on the actual days relative to Baseline. All visits will be assigned a target study day. For the determination of target days, weeks will be assumed to have 7 days. Baseline will have a target study day of 1. Thus, following Week x would have a

target day of $x \times 7 + 1$. For each assessment, the post-baseline period will be divided up using the scheduled visit's target days. The lower bound of each visit interval will be calculated as the mid-point between the target day and the previous visit's target day in the following manner: study day interval lower bound = target study day - ((target study day - last target study day) / 2). Since each assessment has its own schedule, the study day interval needs to be defined separately according to the SoA listed in Section 9.1. See below Table 2 for an example of Vital Signs.

Table 2: Analysis Visit Windows (Example of Vital Signs)

Scheduled Visit Week	Target Study Day	Study Day Interval
Baseline	1	The last measurement on or prior to the first dose of study drug
Week 4	29	2 to 35
Week 6	43	36 to 49
Week 8	57	50 to 70
Week 12	85	71 to 105
Week 18	127	106 to 147
Week 24	169	148 to 210
Week 36	253	211 to 294
Week 48 (without Extension)	337	295 to 350
EOS (without Extension)	365	351 to the last date of patients don't enter Extension
Week 48 (with Extension)	337	295 to 378
Week 60	421	379 to 462
Week 72	505	463 to 546
Week 84	589	547 to 630
EOS (with Extension)	673	631 to the last date of patients enter Extension

Abbreviations: EOS = end of study

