	Extension Period Day 365 added to EOS visit	Correction of typographical error.
	Administer/dispense ALXN1840 deleted at Extension Period Day 337.	Extension Period Day 337 is the last visit in the Extension Period; treatment with ALXN1840 is complete.
Section 5.1, Inclusion Criteria	Inclusion criterion #1 for confirmation of diagnosis of Wilson disease changed to Leipzig score ≥ 4 (formerly > 4) and expanded to include historical test results.	A historical diagnosis of Wilson disease is sufficient. The original criteria for diagnosis of Wilson disease will be recorded in a case report form. It is not necessary to repeat the diagnostic evaluation of Wilson disease for this protocol.
Section 5.1, Inclusion Criteria; Section 8.3.5, Pregnancy; Section 10.4, Appendix 4, Pregnancy Information	Contraception guidance updated to include duration of use and type; duration of pregnancy follow-up revised.	To further define contraception and pregnancy follow-up requirements.
Section 5.2, Exclusion Criteria	Criterion #17 amended to exclude participation in another clinical study within 3 months (or 5 half-lives of the administered investigational medicinal product, whichever is longer) prior to study start.	More detailed language regarding exclusion of patients who participated in any interventional study prior to initiation of Study ALXN1840-WD-205.
Section 6.5, Concomitant Therapy	Standard of care treatment for Wilson disease added as prohibited medication during the Treatment and Extension Periods.	Standard of care treatment for Wilson disease and ALXN1840 should not be administered concomitantly.
Section 6.6, Dose Modification, Table 6	Addition of dose modification rules for increased triglycerides and total cholesterol.	To include guidance on dose modifications in the event of increased triglycerides or total cholesterol.
Section 8, Study Assessments and Procedures	Liver biopsy text revised to “Liver biopsy is the last pre-dose baseline procedure to be completed and must be completed within 14 days prior to the first dose of ALXN1840” (formerly “a minimum of 14 days”).	To align with text in Section 8.6.

Section 8.6, Pharmacodynamics	Text updated to include all pharmacodynamic measures that will be evaluated.	For clarification and completeness.

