1.3. Schedules of Activities

The Schedule of Activities (SoA) for the Screening and Treatment Periods is provided in [Table 1](#). In the Screening Period, the liver biopsy should be performed after all other screening activities have been completed, including imaging, and the patient has met all inclusion and no exclusion criteria.

The Day 337 (Week 48) visit is the end of the Treatment Period and the beginning of the Extension Period (ie, the Week 48 visit and the Extension Period Day 1 visit will occur on the same day). All assessments for the Week 48 visit and the liver biopsy must be performed before the first dose of ALXN1840 on Day 1 of the Extension Period. Dosing of ALXN1840 on Extension Period Day 1 marks the beginning of the Extension Period. Patients who do not enter the Extension Period will discontinue dosing at Week 48 following the second liver biopsy and will have a final study visit for safety follow up at Day 365 (Week 52) of the Treatment Period.

The SoA for the Extension Period is provided in [Table 2](#).

On study visit days where laboratory sampling is planned, patients will be asked to withhold any doses of ALXN1840 due to be taken prior to their visit, to allow laboratory samples to be taken pre-dose.

Laboratory specimen handling and processing instructions will be provided in the study laboratory manual. Blood samples should not be collected from a heparinized line.

Unscheduled visits that occur outside the protocol-specified visits are permitted at the discretion of the Investigator. Procedures, tests, and assessments conducted during unscheduled visits will be performed at the discretion of the Investigator.

Table 1: Schedule of Activities –Treatment Period

	Screening	Treatment Period													UNS ^a	Follow-Up ^b	
Day	-28 to -1	1 ^c	8 ^d	15 ^d	29 ^e	43 ^e	57 ^e	85 ^e	127 ^e	169 ^e	211 ^d	253 ^e	295 ^d	337 ^e / ET ^e		365	
Week	-4 to 0		1	2	4	6	8	12	18	24	30	36	42	48		52	
Window (days)			±3										±7	±3	±7		±7
Obtain informed consent (written or electronic)	X																
Review eligibility criteria	X ^f																
Medical history ^g and demographic parameters ^h	X																
WD medication history	X	X															
Physical examination	X													X		X	
Abbreviated physical examination ⁱ		X			X	X	X	X	X	X		X					
Vital signs ^j	X	X			X	X	X	X	X	X		X		X		X	
12-lead ECG	X					X								X			
FSH ^k	X																
HIV/hepatitis B and C testing	X																
DNA sample		X ^l															

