- ⁱ Plasma samples will be obtained from the blood samples collected pre-dose on the day of all study visits. Patients should be instructed not to take their dose of ALXN1840 on the morning of scheduled study visits so that PK/PD/Biomarker samples are collected at pre-dose trough: total and PUF Mo (PK), total and PUF Cu, NCC (PD), Cp, and CpC (biomarker).
- ^j The UWDRS is scheduled to be performed at Extension Period Day 1 and Day 337 (Week 48) only but can also be performed as appropriate if a neurological adverse event is reported.
- ^k ALXN1840 will not be dispensed or administered at the ET Visit.

Abbreviations: BPRS = Brief Psychiatric Rating Scale-24; CGI-I = Clinical Global Impression-Improvement Scale; CGI-S = Clinical Global Impression-Severity Scale; CLDQ = Chronic Liver Disease Questionnaire; EOS = End of Study; EQ-5D = EuroQoL 5 Dimensions; ET = Early Termination; ICF = informed consent form; MELD = Model for End-Stage Liver Disease; MRE = magnetic resonance elastography; MR-PDFF = magnetic resonance-proton density fat fraction; PD = pharmacodynamic; NCC = non-ceruloplasmin bound copper; PK = pharmacokinetic; SF-36 = Short Form 36; TSQM-9 = Treatment Satisfaction Questionnaire for Medication-9; UNS = unscheduled; UWDRS = Unified Wilson Disease Rating Scare; WD = Wilson Disease

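### SAP Table 2 labels Day 673 as the extension EOS and has no Week 96 row, although Amendment 5 places that EOS visit at Extension Day 365, which is study Day 701

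*SAP*

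**What the plan says.** **SAP 9.4.4.** Data summarised by visit are reassigned to analysis windows. Week x has target day 7x + 1, and each window starts at the mid-point between its own target and the previous one. Table 2 works this through for vital signs. For patients in the extension it goes from Week 84 (target 589, Days 547 to 630) straight to EOS (with Extension), target 673, window "631 to the last date of patients enter Extension". For patients who do not enter the extension it has two separate rows: Week 48 (target 337, Days 295 to 350) and EOS (target 365, from Day 351).

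**SAP 7.3.3.1 and 7.3.3.3.** When a window holds several laboratory or vital-sign records, the one nearest the target day is summarised, and the later one if there is a tie.

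**Protocol 1.3.** The two periods share a day: "the Week 48 visit and the Extension Period Day 1 visit will occur on the same day". That day is study Day 337. Patients who stop at Week 48 "will have a final study visit for safety follow up at Day 365 (Week 52) of the Treatment Period".

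**Protocol summary of changes, current amendment, entries for the extension schedule.** One entry reads "Extension Period Day 365 added to EOS visit". Another gives as the reason for removing dispensing at Extension Day 337 that "Extension Period Day 337 is the last visit in the Extension Period; treatment with ALXN1840 is complete".

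**Protocol 1.3, extension schedule footnotes.** Extension Day 337 is an assessment visit: "The UWDRS is scheduled to be performed at Extension Period Day 1 and Day 337 (Week 48) only".

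**The concern.** The last row of Table 2 carries the name of one visit and the day of another. Its target is the end-of-treatment visit, and its label is that of a follow-up visit four weeks later. Its open-ended window takes in both.

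The extension exists to describe longer-term safety and efficacy, and by-visit tables are a main way of reporting it. Under the nearest-record rule, a reader of the EOS row would take end-of-treatment values for follow-up values. The follow-up values of the same patients would be absent from the by-visit table, and Week 96, the planned end of the 48-week extension, would have no row of its own. For a patient without a Week 96 record, the follow-up value would fill the row. The row could then combine on-treatment and off-drug values from different patients with nothing to show it.

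**Working it through.** **Inputs.** Target rule, mid-point rule and Table 2 rows: SAP 9.4.4. Shared day 337: Protocol 1.3. Extension Days 337 and 365: the current amendment's summary of changes, with Day 337 also in the footnotes to the extension schedule.

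**1. Reproduce the SAP row.** The rule is "For the determination of target days, weeks will be assumed to have 7 days", so Week 96 has target 96 × 7 + 1 = 673. The lower bound is 673 − (673 − 589)/2 = 673 − 42 = 631. Both match Table 2. The other lower bounds also reproduce, except Week 4: its mid-point is 29 − (29 − 1)/2 = 15, but the table starts at Day 2 because this is the first post-baseline window. The row is therefore computed correctly for Week 96.

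**2. Convert extension days to study days.** Study day = extension day + 336.

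| Extension day | Study day | Week, (study day − 1)/7 | Row in SAP Table 2 |
|---|---|---|---|
| 85 | 421 | 60 | Week 60 |
| 169 | 505 | 72 | Week 72 |
| 253 | 589 | 84 | Week 84 |
| 337 | 673 | 96 | labelled EOS |
| 365 | 701 | 100 | none |

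**3. Apply the selection rule.** Days 673 and 701 both fall in the window from Day 631. Their distances from the target are 0 and 701 − 673 = 28.
- Both records present: the Day 673 value is shown as EOS, and the Day 701 value is not in the by-visit row.
- Day 673 record missing and no other record nearer: the Day 701 value is shown as EOS.

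**4. Windows with two rows.** The EOS lower bound is 701 − (701 − 673)/2 = 701 − 14 = 687. Week 96 then runs from 631 to 686 and EOS from 687 onward. Week 84 stays at 547 to 630.

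**5. Changing only the target does not work.** With EOS at 701 and no Week 96 row, the lower bound is 701 − (701 − 589)/2 = 645. Day 673 still falls in the EOS window, and Week 96 still has no row.

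**6. Compare with the planned duration.** Screening 4 + treatment 48 + extension 48 = 100 weeks. A follow-up four weeks after the extension makes 104. The Week 100 in the table above is counted from the first dose, so it is not the same 100 weeks.

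**The case against.** **Day 701 rests on limited text.** The extension EOS day comes from one line of the amendment's summary of changes plus the shared Day 337. The grid of protocol Table 2 could not be read in the copy reviewed, so it is not confirmed that vital signs, or any other assessment, fall at both Extension Day 337 and Day 365. This stands, and it makes the finding conditional. The line does, however, describe what the current amendment put into the schedule that SAP 9.1 adopts, and the same summary treats Extension Day 337 and the EOS visit as separate entries.

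**Other text points to Week 96 as the end.** The duration of about 100 weeks (Protocol 1.1 and 4.1, SAP 4) leaves no room for a later visit, and Protocol 4.4 ties the end of study to the last visit of the 48-week Extension Period. This too stands, as an inconsistency to settle. SAP 7.3.1, which stops study duration at Week 96, is weaker evidence: it also stops at Week 48 for patients who, under Protocol 1.3, have a Week 52 visit.

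**Table 2 is an example.** SAP 9.4.4 says each assessment's windows follow its own schedule, so correct programming from the schedule could separate the two visits. That limits the reach of the error. It does not correct the vital-signs row, which is the only worked model.

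**Stronger readings that a reader might draw.** One is that all follow-up data are discarded. They are not: the last available value enters the last-assessment summaries for laboratory tests and vital signs, laboratory worst-value summaries use all post-baseline data, and all extension data are listed (SAP 7.3.3.1, 7.3.3.3, 7.4). Another is that on-drug and off-drug values are pooled throughout. The rule takes one record per patient and window, so mixing arises only across patients, when the off-drug record is the one nearest Day 673. Adverse-event summaries do not use these windows.

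**Conclusion.** The row needs correcting. Day 673 is Week 96 by the SAP's own rule, and the EOS visit listed in Amendment 5 converts to Day 701. One row labelled EOS covers both, and Week 96 has none. The split that Table 2 makes for patients outside the extension is missing for those in it.

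The gap is 28 days. It concerns each patient with a record at both visits, or only at the later one, for each assessment scheduled at both. The number of patients is not known in advance. The plan expects about 24 to complete the Treatment Period, and the extension is optional.

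The effect is confined to by-visit descriptive tables for the extension. The Week 48 windows and the primary analysis of liver copper do not depend on this row.

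The conclusion assumes that the Amendment 5 extension schedule has an EOS visit at Extension Day 365, and that the assessment concerned is done there as well as at Extension Day 337. A reader might infer that Table 2 contains an arithmetical slip or that Day 701 is beyond doubt. The documents support neither: 673 and 631 are computed as the rule requires, and the duration and end-of-study text do not yet agree with a visit on Day 701.

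**What to change.** 1. Confirm against protocol Table 2 (Amendment 5) which assessments are scheduled at Extension Day 337, at Extension Day 365, or at both.
2. If vital signs are scheduled at both, replace the last row of SAP Table 2 with two rows:

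| Visit | Target day | Window |
|---|---|---|
| Week 96 | 673 | 631 to 686 |
| EOS (with Extension) | 701 | 687 to last date |

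3. Make the same split only for assessments scheduled at both visits. For those done at one of them, use that visit's name and day, so that no empty row or wrong window is created.
4. Reconcile the 100-week duration (Protocol 1.1 and 4.1, SAP 4) and the end-of-study definition (Protocol 4.4) with the EOS visit day.

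The cost is a check of the schedule, two table rows, the matching programming of the windows, and a clarification of the duration text. No data collection changes.
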